13.2 Analysis Populations

Analysis will be based on the following populations:

13.2.1 Enrolled Set

The enrolled set (ES) includes all patients who provided informed consent.

13.2.2 Full Analysis Set

The full analysis set (FAS) includes all patients with at least one IMP administration.

13.2.3 Pharmacokinetic Analysis Set

The pharmacokinetic analysis set (PKS) will include all patients with an evaluable 24-hour PK profile and no major protocol deviations with an impact on PK analysis.

13.2.4 Safety Set

The safety set (SS) includes all patients with at least one IMP administration. The FAS and the SS are identical.

13.2.5 Procedures for accounting for missing, unused and spurious data

All data will be summarised descriptively using the observed cases; no data imputation other than imputation of missing dates is required.

Imputation rules for partially or completely missing dates will be specified in the SAP.

13.3 Determination of Sample Size

The clinical study BIA-51058-201 was designed to explore for the first time the pharmacokinetics, safety and efficacy of zamicastat in PAH patients in its potential therapeutic dose range (50 mg to 200 mg). Since this is an exploratory and descriptive study and no powered comparative statistical analysis is planned, study sample size was not formally calculated. Thus, it was considered that 32 patients constitute an appropriate sample to meet the objectives of the study, considering the low prevalence of the disease and the consequent recruitment constrains.

13.4 Statistical Methods

13.4.1 Analysis of primary pharmacokinetic endpoints

The primary analysis of this study will be the analysis of the PK parameters derived by non-compartmental analysis from the plasma drug concentration versus time using Phoenix WinNonlin v8.0 or a more recent version (Certara USA, Inc., USA). Actual sampling times will be used. The area under the plasma concentration-time curve from time zero to 24 hours post-dose will be calculated using the linear trapezoidal rule.

Summary statistics will be reported, as appropriate, using the geometric mean, arithmetic mean, standard deviation, coefficient of variation, median, minimum, and maximum.

Further details of the statistical analysis and reporting of the pharmacokinetic endpoints, such as, assessment of dose proportionality (e.g. C_{maxSS} and $AUC_{0-24hSS}$) and time to steady state using concentration trough levels, will be included in a separate SAP.

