Clinical experience with zamicastat in humans also includes three ongoing phase I clinical studies:

- an open-label, sequential group, multiple-dose study to evaluate the PK, safety, and tolerability of zamicastat in subjects with hepatic impairment and normal hepatic function (BIA-51058-113);
- an open-label, sequential group, multiple-dose study to evaluate the pharmacokinetics, safety, and tolerability of zamicastat in subjects with renal impairment and normal renal function (BIA-51058-114);

- an open-label study to assess the absorption, distribution, metabolism and excretion, including the mass balance recovery, metabolite profiling and identification, of [¹⁴C] labelled BIA 5-1058 following a single oral dose administration in healthy male subjects (BIA-51058-119).

Overall, 571 healthy subjects aged 18 to 73 years, have been enrolled in the completed phase I studies and 512 have been exposed to zamicastat. The highest doses of zamicastat administered in the clinical studies were 2400 mg under single-dose conditions (study BIA-51058-101) and 1200 mg under multiple-dose conditions (studies BIA-51058-101, and 105). On the other hand, the highest single and multiple-dose exposure to zamicastat were achieved with the 1200 mg, micronized API, under fed conditions (BIA-51058-102) and 1200 mg, micronized API, under fasted conditions (BIA-51058-105), respectively.

Pharmacokinetic properties

Systemic plasma exposure of zamicastat increases in a dose-dependent manner and pharmacokinetics indicates to be dose-linear over the dose range of 25 to 400 mg in fed and micronized conditions (BIA-51058-116), despite the moderate to high variability between subjects.

The AUC_{0-t} of total radioactivity in plasma was 91-fold higher than the cumulative concentration of zamicastat and its metabolites (BIA 5-453 and BIA 5-961) in plasma suggesting that other metabolites than BIA 5-453 and BIA 5-961 may be formed during metabolism of zamicastat which have not yet been identified (BIA-51058-104). Moreover, zamicastat and its metabolites demonstrated to be excreted both by faeces and urine, with faeces as the major route (65.3%). Overall, zamicastat plasma exposure is higher in multiple-dose than in single-dose conditions (time-dependent pharmacokinetics), with the mean accumulation ratios (C_{max} and AUC) ranging from 0.963 to 2.597 and 1.095 to 3.462. Zamicastat steady-state is reached between Day 3 and Day 5 following once-daily administration (BIA-51058-104).

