Patients not tolerating their next dose at any time during the 14-days dose finding period will come immediately to the site or call the investigator (unscheduled visit), unless intolerance was detected during a scheduled visit and the dose will be down-titrated to the patient's previous

tolerated dose. Then they will continue this treatment for 42 days during the maintenance period.

The dose which will be taken during the maintenance period will be considered as an individual HTD.

At the end of the maintenance period, the patient will have the opportunity to continue treatment in an extension study (BIA-51058-202), which will be described in a separate protocol.

Patients not tolerating their individual HTD during the maintenance period have to be withdrawn from the study. An overview of the study design is provided in Figure 1.

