10.3 Selection of Doses in the Study

10.3.1 Selection and timing of dose for each patient

Each patient will start treatment with 50 mg zamicastat once daily (Dose A) at visit A1 and will be up-titrated step by step to the individual HTD i.e. up to 200 mg zamicastat once daily. The 100 mg tablet has to be split at the break score in two equal halves using a pill splitter.

Table 2: Dosage regimen

	Daily dose
Dose A	50 mg (half a tablet of 100 mg)
Dose B	100 mg (one tablet of 100 mg)
Dose C	150 mg (one and a half tablet of 100 mg)
Dose D	200 mg (two tablets of 100 mg)

Each next dose will start after 14 days of treatment if the previous dose was considered safe by the investigator. The up-titration is based on the following safety criteria, including but not limited to:

- Absence of symptomatic and/or clinically relevant orthostatic hypotension
- SBP > 95 mmHg or DBP > 50 mmHg
- Absence of clinically significant changes in ECG parameters (heart rate, P-R interval, QRS duration, QT and QTc interval)
- Absence of clinically significant hypersensitivity/skin allergic reactions

Patients not fulfilling the criteria for up-titration after 14 days of treatment with 50 mg zamicastat have to be withdrawn from the trial.

If the patient's next dose will not be tolerated by the patient, the dose has to be down-titrated to his/her previous dose and this dose will be considered as the individual HTD, if tolerated by the patient. Treatment at the individual HTD will be for 42 days during the maintenance period.

Zamicastat has to be taken in the morning after breakfast. The patient must not take the tablet at home on visit days (A3/B3/C3/D3, MPV1, MPV2 and MPV3).

In case a patient missed to take the dose after breakfast, (s)he should take the dose after lunch. The next dose should be taken as scheduled. If the dose was missed after lunch too, the dose for this day has to be skipped.

Patients taking 150 mg or 200 mg of zamicastat and who will not participate in the extension study will take 100 mg zamicastat for 14 days.

In case a patient will discontinue the trial early due to the occurrence of an AE, down-titration is not mandatory, but at the investigator's discretion. In case down-titration is recommended by the investigator, it should follow the same procedure as described above.

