13.1 Variables

13.1.1 Primary endpoint; pharmacokinetics

The following PK parameters (24-hour profile) for zamicastat and its metabolites will be derived after a single dose of 50 mg zamicastat at visit A1 (Day 1):

1. Area under the curve 0-24 h (AUC_{0-24h})
2. Maximum plasma concentration (C_{max})
3. Time until C_{max} (t_{max})

The following PK parameter (24-hour profile) for zamicastat and its metabolites will be derived at steady-state at the individual HTD and will be taken at visit MPV3.

4. Area under the curve 0-24 h ($AUC_{0-24h,SS}$)
5. Maximum plasma concentration ($C_{max,SS}$)
6. Time until $C_{max,SS}$ ($t_{max,SS}$)
7. Minimum plasma concentration at the end of the dosing interval ($C_{min,SS}$)

The following PK parameter (trough level) will be derived for each dose at steady-state.

8. Minimum plasma concentration at the end of the dosing interval ($C_{min,SS}$)

Additional PK parameters may also be calculated if considered appropriate.

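### AUC0-24h,SS and Cmax,SS exist at one tolerability-selected dose per patient, so comparing them across HTD groups could understate dose proportionality if intolerance depends on exposure

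*Protocol*

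**What the plan says.** Section 13.4.1 of the protocol defers the method for dose proportionality to a separate plan and names two parameters as examples: "such as, assessment of dose proportionality (e.g. C_{maxSS} and $AUC_{0-24hSS". Section 13.1.1 fixes when they are measured: the steady-state 24-hour parameters "will be derived at steady-state at the individual HTD and will be taken at visit MPV3". Section 11.6.7 omits the 24-hour profile at an early discontinuation visit.

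The dose at MPV3 follows from titration. Under section 10.3.1, if the next step is not tolerated, "the dose has to be down-titrated to his/her previous dose and this dose will be considered as the individual HTD". Section 8.1 adds: "The dose which will be taken during the maintenance period will be considered as an individual HTD".

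Two other PK sources bear on the question. A 24-hour profile "will be derived after a single dose of 50 mg zamicastat at visit A1 (Day 1") is planned for every patient. Troughs are planned at several doses: "The following PK parameter (trough level) will be derived for each dose at steady-state". SAP section 2.2.1 lists the trough visits as A3, B3, C3, D3, MPV1, MPV2 and MPV3.

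The SAP does not cover PK. It refers to a separate reporting and analysis plan, its Appendix 4.

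**The concern.** Steady-state AUC and Cmax at 50, 100 or 150 mg come only from patients who did not get past the next step. The values at 200 mg come only from patients who passed every step. Dose is thus assigned by tolerability, and tolerability may itself reflect exposure.

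The documents make such a link plausible. The up-titration criteria include "Absence of symptomatic and/or clinically relevant orthostatic hypotension", and section 10.8.3 ties orthostatic hypotension and syncope to the rise in dopamine that zamicastat causes. Section 6.2.2 describes dose-linear exposure from 25 to 400 mg in healthy subjects, "despite the moderate to high variability between subjects". With that much variability, patients with high exposure per mg could stop early and those with low exposure per mg could reach 200 mg.

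The primary objective is the PK profile of different doses, in order to find a dosage range. Sections 6.3 and 8.2 expect that PK may differ in PAH. An apparent flattening over 50 to 200 mg caused only by selection could be read as such a difference.

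**Working it through.** The plan states no slope, criterion or confidence interval for proportionality, so there is no figure to reproduce.

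**1. Where the bias comes from.** Let u be a patient's log exposure per mg, and suppose the drug is exactly dose-proportional:

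log AUCss = a + log(HTD) + u + error

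The slope of log AUCss on log HTD, one point per patient, tends to

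1 + Cov(log HTD, u) / Var(log HTD).

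If high exposure lowers the HTD, the covariance is negative and the slope falls below 1. If tolerability is unrelated to u, the covariance is zero and the slope is 1.

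**2. Possible size.** N = 32 and dose-linearity come from the protocol. Everything else is assumed: between-patient CV 30%, 50% or 70%, within-patient CV 20%, and the tolerance models below.

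*Logistic model.* Intolerance at 200 mg is 20% for a median patient, and its log-odds rise by 1 to 3 per log unit of exposure. There were 600 replicates; 51% to 67% of patients reached 200 mg.

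| Between-patient CV | Mean slope (log-odds 1 to 3) | Coverage of 95% CI |
|---|---|---|
| 30% | 0.90 to 0.66 | 89% to 58% |
| 50% | 0.76 to 0.32 | 78% to 16% |
| 70% | 0.58 to 0.06 | 62% to 4% |

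*Threshold model.* Each patient has an exposure limit with log-SD 0, 0.3 or 0.6, and 50% or 75% of patients reach 200 mg. Large-sample slopes run from 0.78 to -0.41. The fitted 200/50 mg ratio is 4^slope, so it runs from 2.96 to 0.56 against a true 4.0. At CV 50%, log-SD 0.3 and half reaching 200 mg, the slope is 0.25 and the ratio about 1.4. With 32 patients the 90% CI lies wholly below 1 in 43% to 100% of trials.

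*Tolerability independent of exposure.* The slope is 0.99 to 1.00, and the 90% CI lies wholly below 1 in 4% to 5% of trials, the nominal rate.

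**3. Within-patient alternatives on data already planned.**

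- Trough slope with a patient effect: u is absorbed. The slope is 1.00 in every scenario, with SD about 0.04 against 0.12 to 0.30 for the HTD-group slope. Pooling troughs without a patient effect still gives 0.68 to 0.96.
- MPV3/A1 ratio: log(AUCss / AUC at A1) = log(HTD/50) + log(accumulation) + error, so u cancels. The slope is 0.99 to 1.00.

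**4. What these alternatives leave open.** The simulations contain no time effect, but dose and time rise together within a patient. Take troughs at 50, 100, 150 and 200 mg with an assumed upward drift of 10% per 14-day period. Deviations of log dose from their mean are -0.794, -0.101, 0.304 and 0.592, with sum of squares 1.084. Period deviations are -1.5, -0.5, 0.5 and 1.5, and the cross-product is 2.282. The slope is then 1 + 2.282 × ln(1.1) / 1.084 = 1 + 0.2175 / 1.084 = 1.20. That shift is five times the SD of 0.04.

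**The case against.** The plan commits to no particular estimator. The two parameters are only examples, Cmin,SS at each dose is itself a primary parameter, and the PK plan may already use a patient-level model. This stands. A reader might infer that the proportionality result will be biased downward with an interval of poor coverage. The documents do not support that, because the coverage figures above describe a regression on HTD that the protocol never specifies. The file name of the PK plan in SAP section 10 dates it 20 February 2020, before protocol Final 3.0 of 12 May 2020, which is one more reason to check it.

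Exposure-driven intolerance is assumed. Section 6.2.2 reports no clear tolerability trend with rising dose in healthy subjects, section 8.2 places 200 mg six-fold below the highest multiple dose tested, and a skin or allergic reaction need not follow exposure. This also stands, so the bias is only conditional.

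A reader might also take the troughs to be free of confounding. They are not. A patient effect removes selection on exposure per mg, but section 6.2.2 describes time-dependent PK, with AUC accumulation ratios of 1.095 to 3.462. Steady state by Day 3 to 5, against 14-day steps, limits the problem without excluding it. A patient down-titrated between scheduled visits may have no trough at the failed dose, since section 11.7 requires only adverse events and concomitant medication at an unscheduled visit.

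Finally, proportionality is not a listed objective or endpoint, and the study is exploratory. That argues for a modest change, not for none.

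**Conclusion.** The structural point holds. The two parameters named for proportionality can compare doses only between groups selected by tolerability, and nothing in the protocol or SAP adjusts for this. If intolerance depends on exposure, the comparison could be biased toward less-than-proportional exposure; if it does not, there is no bias.

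The size cannot be derived from the documents, which give neither a between-patient CV nor a distribution of HTD. Simulated slopes from about 1.0 down to near 0 or below show what is possible under the assumptions listed, not what to expect. The point concerns the protocol text and remains subject to the PK plan. It is a worthwhile, inexpensive improvement to an analysis that serves the primary objective.

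**What to change.** First check what the separate PK plan specifies. Then, in protocol section 13.4.1 and that plan:

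1. Make a within-patient analysis the main inference on proportionality: a power model of log Cmin,SS on log dose with a patient effect, over A3, B3, C3 and D3. Use the repeat troughs at an unchanged dose (MPV1, MPV2 and MPV3 pre-dose) to check or adjust for time drift.
2. Support it with AUC0-24h,SS and Cmax,SS adjusted for the same patient's 50 mg values at A1, noting that this sets single-dose against steady-state exposure. A constant accumulation ratio goes into the intercept; one that varies with dose or is related to tolerance would leave bias. Also compare A1 exposure across HTD groups, as a direct check for the suspected selection.
3. Report AUC0-24h,SS and Cmax,SS by HTD descriptively. State that differences between HTD groups may be confounded with tolerability and are not by themselves evidence for or against proportionality.

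The cost is one or two extra models and some wording, with no new samples, visits or dosing changes. The drawbacks are that the main inference rests on troughs rather than on AUC or Cmax, and that patients with a trough at only one dose do not inform the within-patient slope.

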13.4.2 Analysis of secondary efficacy endpoints

Efficacy data will be analysed exploratively and will be based on the FAS. Continuous measures will be summarised using summary statistics: mean, standard deviation, median, minimum and maximum, in addition for the changes from baseline a 95% confidence interval will be provided. Categorical variables will be summarised by using frequency counts and percentages.

The scores of each SF-36v2 subscale, as well as the Physical and mental Component summary scores (PCS and MCS), will be described using summary statistics. The derivation of PCS and MCS will be defined in the SAP.

13.4.3 Analysis of secondary safety endpoints

All safety analyses will be based on the SS. Treatment-emergent AEs will be summarised by Medical Dictionary for Regulatory Activities (MedDRA) primary system organ class (SOC) and preferred term (PT).

In addition, TEAEs will be summarised by severity and drug relationship. TEAEs leading to discontinuation from the study, AEs of special interest and serious TEAEs will be summarised in addition. All AEs will be listed.

Laboratory, vital signs and ECG parameters will be described using summary statistics. The incidence of clinically relevant abnormalities in laboratory and ECG results will be described using frequency counts and percentages.

The number of digital scars and skin score in patients with scleroderma will be analysed using summary statistics.

13.4.4 Analysis of secondary pharmacokinetic endpoints

Apparent total clearance (CL/f), terminal half-life ($t_{1/2}$) and apparent volume of distribution (V_z/f) will be described using summary statistics by each dose group. PK analysis will be based on the PKs.

In the PK analysis all concentrations below the limit of quantitation or missing data will be labelled as such in the concentration data listings.

13.4.5 Analysis of secondary pharmacodynamic endpoints

Maximum observed effect on plasma D β H activity (E_{max}), minimal observed effect on plasma D β H activity (E_{min}), time to occurrence of E_{max} (TE_{max}), time to occurrence of E_{min} (TE_{min}) and area under the effect-time curve ($AUEC_{24}$) will be calculated using % inhibition of D β H

activity using Phoenix WinNonlin v8.0 or a more recent version (Certara USA, Inc., USA). Percent inhibition of DβH activity, PD parameter estimates and urinary catecholamine levels (norepinephrine and dopamine) including changes from baseline will be described using summary statistics by each dose group. Pharmacodynamic analysis will be based on the PKS.

Further details of the statistical analysis and reporting of the pharmacodynamic endpoints, such as, dose response modelling for % DβH inhibition and exposure response modelling to assess relationship between drug plasma concentrations and corresponding % DβH inhibition, will be included in a separate Statistical Analysis Plan.

13.4.6 Interim analyses and criteria for the termination of the study

No interim analyses are planned in this study.

The DSMB will periodically review the safety data and is empowered to recommend modifications of the protocol (dosage levels) or to recommend temporary suspension or early termination of the study, if major concerns arise about patient safety at any time during the course of the study.

13.5 Deviations from the Original Statistical Analysis Plan

Any deviation from the original SAP will be described and justified in the final report.

14. DIRECT ACCESS TO SOURCE DATA/DOCUMENTS

The investigator/institution will give the clinical research associate(s) (CRAs) direct access to primary patient data (i.e. source data) which support the data on the eCRFs for the study, i.e. general practice charts, hospital notes, appointment books, original laboratory records, electronic patient files etc. Other authorised persons such as auditors, IEC members and regulatory inspectors will be provided direct access to these source data, too.

14.1 Source Data

Source data is defined as all information in original records and certified copies of original records of clinical findings, observations or other activities in a clinical study necessary for the reconstruction and evaluation of the study. Source data are contained in source documents (original records or certified copies).

14.2 Source Documents

Source documents are defined as original documents, data and records (e.g. hospital records, clinical and office charts, laboratory notes, memoranda, patient diaries or evaluation check lists, pharmacy dispensing records, recorded data from automated instruments, copies or manuscripts certified after verification as being accurate copies, microfiches, photographic negatives, microfilm or magnetic media, x-rays, patient files, records kept at pharmacy, at the laboratories and at medico technical departments involved in clinical study). Source documents comprise documents in paper and electronic format.

14.3 Direct Access

Direct access is defined as the permission to examine, analyse, verify and reproduce any records and reports that are important to evaluation of a clinical study. Any party (e.g. domestic and foreign regulatory authorities, Bial/SCOPE CRAs, IEC members and auditors) with direct access should take all reasonable precautions within the constraints of the applicable regulatory requirements to maintain the confidentiality of patient identities and sponsor proprietary information.

15. DATA HANDLING AND RECORD KEEPING

15.1 Completion of Case Report Forms

Data reported on the eCRF that are derived from source documents should be consistent with the source documents.

All clinical information requested in this protocol will be recorded by the principal investigator or his/her authorised staff in the eCRF in accordance with the study-specific data entry rules. Entries in the eCRFs must be reviewed and verified for accuracy by the principal investigator and signed off with electronic signature.

Periodically, a CRA will review the accuracy, completeness and timeliness of all the data entered in the eCRF against source documents.

No direct entries on the eCRFs (i.e. entries with no prior written or electronic record of data) will be allowed.

